2. Understand perspectives on preemptive PGx testing among key stakeholders in the primary care clinics predominantly serving medically underserved patients. We will conduct in-depth, semi-structured interviews with a subsample of recruited patients from Aim 1 and clinicians within the clinic sites to identify influential factors critical to implementing PGx testing, including motivations, barriers, and best practices for the delivery of results.

3. Identify specific socioeconomic characteristics most strongly associated with PGx drug prescription rates. Our preliminary data using EHR data from UF Health show strong correlations between zip code-derived healthcare geographic access scores and rate of PGx drug prescriptions. We aim to use the results of a validated socioeconomic estimation tool as well as individual measures of socioeconomic status in a single predictive model to determine which social determinants most associate with PGx drug prescription rate within the 100 patients from Aim 1.

6. Research Plan:

Study population and setting. This study will include UF Health patients recruited from clinics that serve mostly medically underserved areas. Primarily, this will include the UF Health Family Medicine Eastside and Main St. Clinics, which serve a large number of low-income, black and Latino patients. Overall, we plan to recruit 100 patients from targeted clinics. Inclusion criteria are designed to identify patients who have a high possibility of benefitting from PGx testing.

Inclusion Criteria:

1. Adults (18 years or older) with active prescriptions for at least 3 medications documented within the EHR.
2. At least 1 drug/drug class that could be informed by the PGx test panel (See Appendix A for complete list).
3. A medication change within the past 6 months (associated with a healthcare provider encounter)
4. Self-identify as black or Latino.

Exclusion Criteria:

1. Patients with any history of PGx testing within the EHR.

Participant Recruitment Methods.

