Patients may be approached for the study in various way including clinic intercepts, study flyers and clinic referrals. The electronic health record will be queried to identify potentially eligible participants using the inclusion/exclusion criteria. Providers (including but not limited to physicians, nurse practitioners, and pharmacists) who care for patients at UF Health will be notified when their patients qualify for the study and will be asked to discuss the study with their patients.

Patients can be recruited by study staff via two methods:

1. Clinic providers or staff ask patients if they are interested in participating and they acknowledge that they are interested.
2. Clinic provider or staff will provide patients an approved flyer and they contact study staff if interested.

If recruitment occurs during a clinic visit, patients meeting eligibility criteria will be approached by a research coordinator about study participation. Patients may also be contacted via phone after their clinic visit if in-person contact is not possible (for example, but not limited to, space limitations due to COVID-19 restrictions).

A research coordinator will review the consent document with the patient prior to enrollment. The consenting process can be in-person or remote via telephone or through electronic means. Prospective research participants will have the opportunity to ask questions before providing consent and will be provided with a signed copy of the consent form.

After providing written informed consent, a DNA sample will be collected from all patients by saliva (via mouthwash swish and expectorate collection) or buccal cell (via buccal brush/swab). If the genotyping fails with initial sample collection, the patients may be mailed a DNA collection kit for saliva or buccal cell sample collection for retesting.

Study design. After eligible participants provide written informed consent and are enrolled, a DNA sample will be obtained for PGx testing and questionnaires (as described below) will be administered at baseline, and then again at 3 months and 6 months after PGx results are entered into the EHR. Information will be abstracted from the EHR including PGx test results, medication changes, and healthcare provider encounters over the 6-month study duration (Table 1). A 1-month window will be permitted for each follow-up study interaction (\pm 15 days of exact due date).

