PGx testing will be completed using the GatorPGx panel, which is already available for clinical use in the CAP/CLIA certified UF Molecular Pathology Laboratory. Once results are entered into the EHR, Clinical Decision Support Best Practice Advisories already built into Epic will alert providers if a PGx interaction

might occur with a medication they prescribe. All clinical medication decisions will be made at the discretion of the healthcare provider.

Feasibility data collection:

The primary feasibility outcome will be change in patient treatment satisfaction between baseline and 6 months after PGx testing. This patient reported outcome will be measured via the Treatment Satisfaction Questionnaire for Medication (TSQM). The TSQM is a validated tool that assesses three medication-related domains (effectiveness, side effects, and convenience) to synthesize a global satisfaction score.^{5,6} Both global satisfaction and scores from individual domains will be analyzed.

Table 1. Proposed outcomes/measures to be tested

Outcome/Measure	Data source/Instrument	Ascertainment method	Baseline	3 mo.	6 mo.
Implementation Outcomes					
Treatment satisfaction	Treatment Satisfaction Questionnaire for Medication (TSQM)	Online or by phone	X	X	X
Medication adherence	Adherence Questionnaire	Online or by phone	X	X	X
Perceived value	Patient reported value	Online or by phone	X	X	X
Time discussing meds w/ healthcare provider	Patient reported estimate	Online or by phone	X	X	X
Effectiveness Outcomes					
Medication changes	EHR data	EHR data pull	X		X
Provider encounters	EHR data	EHR data pull	X		X
Socioeconomic Measures					
SEI	Patient report	Online or by phone	X		
Occupation	Patient report	Online or by phone	X		
Education level	Patient report	Online or by phone	X		
Household Income	Patient report	Online or by phone	X		
Household zip code	Patient report	Online or by phone	X		

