An important secondary outcome assessing efficacy will include the number of medication changes within the 6-month follow-up period. Medication changes will be defined as the addition, removal, or dosage change to any PGx medication or medication within the same drug class. Comparisons of this outcome should estimate differences in trial-and-error drug dosing that is traditionally used in practice. These outcomes are important because if the results suggest that preemptive PGx testing is associated with increased patient treatment satisfaction, a reduction in medication changes, or increased perceived value of PGx testing, these findings would support expanded clinical implementation in medically underserved patients. This might also suggest that PGx could be further used as a tool to minimize disparities in pharmacotherapy. Other secondary outcomes that will be analyzed include: The prescriber acceptance rate of PGx EHR alert recommendations, number of encounters with a healthcare provider over the study period, genotype turnaround time, and estimated time spent discussing medications with a healthcare provider. These outcomes will be used to assess feasibility and will inform design of a large clinical trial to be funded by future grants.

Socioeconomic data collection: We have previously observed significant associations between calculated geographic access scores and rate of PGx drug prescriptions, which considerably strengthened in subanalyses by race. Whether this association is exclusively related to geography and race or whether it is also related to socioeconomic determinants is unknown. Thus, we will test whether socioeconomic status is a social determinant of health related to PGx drug usage. Patients will answer survey questions related to their education, employment, and income (Table 1).

Qualitative data collection: An estimated sample size of 20 patients from the 100 recruited participants will be recruited for this aim. Patient sampling will be aimed at achieving an approximately even distribution of sex (male and female) and race (Latino and black).

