Analysis plan. For Aim 1, implementation outcomes such as prescriber acceptance, turnaround time, and cost will be assessed using descriptive statistics. Differences in patient reported outcomes such as treatment satisfaction, perceived value, and effectiveness outcomes (Table 1) will be initially compared between baseline and 6 months using Student's t-test or Mann-Whitney U test, depending on the data distribution. In addition to univariate analyses, multiple regression models will also be completed for each outcome, adjusted for potential covariates, such as age, race, sex, clinic site, and Charlson Comorbidity Index. In all analyses, a two-sided $P \leq 0.05$ will be considered statistically significant, and all statistical analyses will be completed in R ver. 3.6.3.

For Aim 2, interview transcripts will be managed using data management software (e.g., Nvivo or Atlas.ti). Data will be thematically analyzed using the widely used constant comparative method.¹³ This systematic approach involves several coding steps including identifying concepts and assigning codes, 2) grouping categories of emergent themes, and 3) axial coding to identify thematic properties. To ensure similarities and differences between patients' experiences can be captured, data analysis will be segmented by group and triangulated with survey data collected from healthcare providers (via separate protocol). Triangulation of data between sources also enhances the validity of the findings.¹⁴ Multiple coders, trained in the CCM approach, will conduct the analysis to ensure rigor. Meetings will be held to compare independent coding, discuss differences in interpretation, collapses analyses, and continuously refine the codebooks. Codebooks will be developed with each stakeholder group dataset. Once codebooks are finalized and analyses complete, each analysis will be validated by an additional coder analyzing a subset of the transcripts from each group.¹² Operational and thematic memos will be maintained across data collection and analysis to ensure researcher reflexivity, thematic saturation, and rich description of themes.

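### No Aim 1 analysis allows for correlation among patients who share a prescriber; once within-patient change is analysed, positive correlation of this kind makes standard errors too small

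*Combined protocol and SAP*

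**What the plan says.** All references are to section 6 (Research Plan) of the combined protocol and SAP.

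- Study population and setting: "Overall, we plan to recruit 100 patients from targeted clinics". Two sites are named: "Primarily, this will include the UF Health Family Medicine Eastside and Main St. Clinics". Neither the total number of clinics nor the number of prescribers is given.
- Study design: "Once results are entered into the EHR, Clinical Decision Support Best Practice Advisories already built into Epic will alert providers if a PGx interaction" could arise with a drug they order. The text then leaves every medication decision to the provider.
- Feasibility data collection: "The primary feasibility outcome will be change in patient treatment satisfaction between baseline and 6 months after PGx testing", measured with the TSQM. Medication changes and provider encounters are secondary outcomes.
- Analysis plan, Aim 1: baseline and 6 months are compared by Student's t or Mann-Whitney U according to the distribution. The word paired does not appear. After that, "multiple regression models will also be completed for each outcome, adjusted for potential covariates, such as age, race, sex, clinic site, and Charlson Comorbidity Index". One significance rule covers every test and model: "a two-sided $P \leq 0.05$ will be considered statistically significant".

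The plan names no prescriber term, random effect, generalised estimating equation, clustered standard error, ICC or design effect.

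**The concern.** Whether an alert leads to a changed prescription depends on the prescriber. A prescriber who acts on most alerts may shift medication changes, encounters and satisfaction for all of their patients; one who overrides most may shift none. With 100 patients drawn mainly from two clinics, many could share a prescriber, and their changes would then not be independent.

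The standard error of a mean change computed as if patients were independent leaves out the variation between prescribers. That matters when the result is carried to other prescribers, and the plan intends this: under Feasibility data collection, favourable findings are to be taken as grounds for wider use in underserved patients, and the outcomes are to inform a larger trial. The size of prescriber-level variation is a planning input for that trial, and without a prescriber identifier the pilot cannot estimate it.

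Clinic site as a fixed covariate can absorb differences between clinics. It does nothing for differences between prescribers within a clinic, and the univariate tests do not include it.

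**Working it through.** **Inputs from the documents.** n = 100; two-sided alpha = 0.05; primary outcome is change within patients. There is no power, effect size, SD or ICC, so the sample size cannot be reproduced. The only stated figure to start from is the 5% level, which corresponds to a critical value of 1.96.

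**Assumptions.** 10 to 20 prescribers with equal numbers of patients (m = 100/number of prescribers); ICC of the change score 0.01 to 0.10; correlation rho between baseline and 6 months of 0.5. The relevant ICC is that of change, because differencing removes stable differences between prescribers.

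**Step 1: paired analysis that ignores prescriber.**
Design effect DEFF = 1 + (m - 1) × ICC. Effective n = 100/DEFF. The true standard error is √DEFF times the computed one. True level = 2 × [1 - Φ(1.96/√DEFF)].

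| Prescribers | m | ICC | DEFF | Effective n | SE ratio | True level |
|---|---|---|---|---|---|---|
| 20 | 5 | 0.01 | 1 + 4 × 0.01 = 1.04 | 96 | 1.02 | 5.5% |
| 20 | 5 | 0.05 | 1 + 4 × 0.05 = 1.20 | 83 | 1.10 | 7.4% |
| 20 | 5 | 0.10 | 1 + 4 × 0.10 = 1.40 | 71 | 1.18 | 9.8% |
| 10 | 10 | 0.01 | 1 + 9 × 0.01 = 1.09 | 92 | 1.04 | 6.0% |
| 10 | 10 | 0.05 | 1 + 9 × 0.05 = 1.45 | 69 | 1.20 | 10.4% |
| 10 | 10 | 0.10 | 1 + 9 × 0.10 = 1.90 | 53 | 1.38 | 15.5% |

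Simulation of the paired t-test with 10 prescribers, ICC 0.05 and rho 0.5 (20,000 replicates) gave 10.5%, against 10.4% by formula.

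**Step 2: the same data under an unpaired t-test, the literal reading.**
Ignoring the pairing overstates the variance by 1/(1 - rho), so the ratio of true to computed variance is V = (1 - rho) × DEFF. True level = 2 × [1 - Φ(1.96/√V)].

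- No clustering, rho 0.5: V = 0.50; about 0.6% in simulation.
- 10 prescribers, ICC 0.05, rho 0.5: V = 0.5 × 1.45 = 0.725; 2.1% by formula, 2.3% in simulation.

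The two errors cancel when DEFF = 1/(1 - rho), that is, ICC = rho/[(1 - rho)(m - 1)]. At rho 0.5 this is 1/9 = 0.11 with 10 prescribers and 1/4 = 0.25 with 20. Below these values the unpaired test is conservative; above them it is liberal. The Mann-Whitney test was not simulated.

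**Step 3: does a prescriber-level analysis restore the level?**
A t-test on prescriber mean changes, with 10 or 20 equal-sized prescribers and ICC 0.05 or 0.10, rejected in 4.8% to 5.3% of simulated null trials.

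**The case against.** The strongest objection concerns direction. A reader might infer that the planned P values are simply too small. The documents do not support that: Step 2 shows that the tests as named, read as independent-samples tests, can be well below 5%. This stands, and it limits the claim. It does not rescue the plan, because the primary outcome is change within patients. Correcting the pairing alone, with 10 prescribers, ICC 0.05 and rho 0.5, moves the level from about 2% to about 10%, so both matters should be settled together.

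A reader might also infer that the intervention acts only through alerts to the prescribers of a few clinics. The text does not say so. Alerts go to whoever prescribes, and under Participant Recruitment Methods, "Providers (including but not limited to physicians, nurse practitioners, and pharmacists) who care for patients at UF Health will be notified", with no limit to the recruiting clinics. Patients' perceived value is also an outcome. One patient may therefore have several prescribers, and any single prescriber field is only a proxy for the cluster.

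Two extensions are tempting and should not be made. The first is to apply these design effects to Aim 3. They apply to a mean. For a slope on a patient-level socioeconomic measure the factor is roughly 1 + (m - 1) × ICC of the measure × ICC of the outcome. With m = 10 and both assumed to be 0.05, this is 1 + 9 × 0.0025 = 1.02, a level of about 5.3%. The second is that repeated alerts distort "The prescriber acceptance rate of PGx EHR alert recommendations". Nothing in the documents says that alerts re-fire or that the denominator is alerts, and the outcome is only described, so there is no test to distort.

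Finally, this is a single-arm feasibility pilot with individual enrolment and no allocation by cluster, and clinic site is already listed as a covariate. That is fair, and it is why a sensitivity analysis is enough.

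**Conclusion.** The gap is real and its consequence is conditional. No Aim 1 test or model accounts for patients sharing a prescriber. Whether the plan as written gives P values that are too small or too large cannot be said, because pairing is unspecified and neither rho, the ICC nor the number of prescribers is given.

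With a within-patient analysis and positive prescriber-level correlation in change, standard errors are too small for any claim that reaches beyond these prescribers. Across the assumed range the understatement is slight at the low end (factor 1.02) and material at the high end (factor 1.38). With ICC up to 0.05, the true standard error is at most about 20% larger than the computed one. All of these figures rest on assumed inputs and equal cluster sizes. The point is worth acting on because the remedy is cheap and the pilot is meant to inform a larger trial, not because the primary result is shown to be invalid.

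**What to change.** In the Analysis plan for Aim 1:

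1. State that baseline and 6 months are compared within patients: paired t-test, Wilcoxon signed-rank test, or a change-score or mixed model.
2. Add each patient's usual prescriber at enrolment to the EHR data pull, and describe it as a proxy for the cluster.
3. Add a sensitivity analysis of change in TSQM, medication changes and encounters with a prescriber random effect, or prescriber-clustered standard errors with a small-sample correction. Keep clinic as a fixed effect, because about two clinics are too few to serve as clusters.
4. Report the prescriber ICC of change, with its uncertainty, for planning the larger trial.

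The cost is one extra EHR field and a few sentences. The downside is somewhat wider intervals, and an imprecise ICC if prescribers are few.

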For Aim 3, total scores and scores within individual domains will be compared with number of medications prescribed, number of healthcare encounters, and PGx drug prescription rate. Comparisons will be completed in univariate analyses via Spearman's correlation test. In addition, multiple regression models will be developed to allow the ability to adjust for potential confounders such as age, and Charlson Comorbidity index. In addition, we will estimate the proportion of variation in PGx prescription rate that can be explained by each socioeconomic measure by comparing coefficients of determination (r^2) in each model.

7. Possible Discomforts and Risks:

Risks involved with participating in this study are minimal, and include accidental disclosure of PHI. To safeguard against this, electronic data will be stored in a custom-designed REDCap database, which is encrypted and password-protected. Paper documents and other physical media will be stored in a

locked cabinet within the PI's locked, private office or the secure Precision Medicine Program research office. Due to the nature of the study, adverse events are not anticipated. However, if any events are observed, they will be reported to the IRB in a manner consistent with UF regulations.

8. Possible Benefits:

Subjects may not directly benefit from participating in this study. There is a possibility of direct benefit to individual subjects, as genotype information could lead to more effective drug prescribing. Nevertheless, in the absence of a direct benefit, the study may advance the field by providing an increased understanding of the utility of preemptive PGx testing in traditionally underserved patient populations. Such understanding is deemed essential for broader dissemination of PGx into clinical care.

9. Conflict of Interest:

The investigators have no conflicts of interest to report. Publications that may result from such research could enhance the reputation of the investigators, but are not expected to affect the conduct of this research.

10. References:

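### Aim 3's models do not commit to holding geographic access or black/Latino group fixed, and comparing raw r² neither isolates each measure's share nor allows for differing degrees of freedom

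*Combined protocol and SAP*

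**What the plan says.** Section 5 (Specific Aims, Aim 3) reports "strong correlations between zip code-derived healthcare geographic access scores and rate of PGx drug prescriptions" from preliminary data. It proposes to use a socioeconomic estimation tool "as well as individual measures of socioeconomic status in a single predictive model", and the purpose is "to determine which social determinants most associate with PGx drug prescription rate" in the 100 Aim 1 patients.

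Section 6 (Socioeconomic data collection) recalls the earlier link with geographic access, "which considerably strengthened in subanalyses by race", and then states the gap: "Whether this association is exclusively related to geography and race or whether it is also related to socioeconomic determinants is unknown". The data to be collected follow: "Patients will answer survey questions related to their education, employment, and income". Table 1 lists household zip code among the socioeconomic measures.

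Section 6 (Analysis plan, Aim 3) begins with unadjusted Spearman correlations and continues: "multiple regression models will be developed to allow the ability to adjust for potential confounders such as age, and Charlson Comorbidity index". For variance explained it says "we will estimate the proportion of variation in PGx prescription rate that can be explained by each socioeconomic measure by comparing coefficients of determination", across several models. It gives no base model, no increment, no adjusted or partial r², and no coding of occupation, education or income. For Aim 1 the same Analysis plan does name race and clinic site as possible covariates; for Aim 3 it names neither.

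**The concern.** The plan itself identifies geography and race as the competing explanations, yet the Aim 3 analysis text does not commit to either as an adjuster. If the models contain only the named covariates, a socioeconomic measure can look associated merely because it tracks access to care, and the question that motivated the aim stays open.

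The r² step raises two further problems. If the r² of a whole model is read as the proportion explained by the socioeconomic measure, it includes what age and Charlson index explain. Also, raw r² never falls when terms are added, so a measure entered as several indicator variables gains an advantage by chance over one entered as a single score. The deliverable is a ranking meant to inform later studies, so a ranking that partly reflects coding could misdirect them.

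**Working it through.** The documents give no r², correlation, effect size or coding for Aim 3, so there is no planned figure to reproduce. What follows illustrates size under stated assumptions.

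**Inputs from the documents.** n = 100 (section 5, Aim 3); two-sided 0.05 (section 6, Analysis plan); named covariates age and Charlson index.

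**Assumptions.** Continuous outcome with variance 1, least squares, complete data, and a base model explaining 0.20 of variance (0.10–0.30 tried).

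1. *Whole-model r².* Add a measure with no effect and 1 degree of freedom (df) to age and Charlson. In simulation the whole-model r² averages 0.22 (0.13–0.32 for a base of 0.10–0.30), although the measure's own share is zero.

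2. *Raw increment of a null measure.* With k df, the expected increment is approximately (1 − base r²) × k/(n − 1).
   - k = 1: 0.80 × 1/99 = 0.008.
   - k = 4 (five categories): 0.80 × 4/99 = 0.032.
   - Simulation over a four-covariate base gives the same values. With adjusted r² = 1 − (1 − r²)(n − 1)/(n − 1 − p), where p is the number of model terms, the average null increment is 0.000 for both.

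3. *Ranking.* Compare a null five-category measure with a 1-df measure that truly adds 0.04, over a four-covariate base of 0.20 (8,000 simulated trials). The null measure ranks higher in:
   - about 40% by raw r² if dummy-coded (36–45% across bases of 0.30–0.10);
   - 16% by adjusted r² if dummy-coded (14–18%);
   - 11% by raw r² if entered as one ordered score.

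   When all measures have the same df over the same base, adjusted r² is the same increasing function of raw r² for each, so the rankings are identical.

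4. *Access left out.* Take a measure with no direct effect, correlating 0.5 with access, and let access correlate 0.1 or 0.2 with the outcome. Age and Charlson explain 0.20.
   - Induced slope = product of the correlations: 0.5 × 0.1 = 0.05, or 0.5 × 0.2 = 0.10.
   - Shift of the test statistic ≈ slope × √96/√(0.80 − slope²), with 96 = 100 − 4 residual df: 0.05 × 9.80/0.893 = 0.55, and 0.10 × 9.80/0.889 = 1.10.
   - Probability that |Z| exceeds 1.96 after that shift: 0.085 and 0.197.
   - Simulation agrees (about 8–9% and 19–20%). With access and black/Latino group in the model the rate is about 5%.

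**The case against.** The strongest case against has three parts.

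*The aim is a ranking.* Section 5 asks which determinants associate most strongly. The geography-and-race sentence in section 6 is motivation, and the sentence after it proposes only to test whether socioeconomic status is related to PGx-drug use. For an aim of plain association, a measure that tracks access is not a false positive. This stands: the rates in step 4 are error rates only if geography is a confounder. If socioeconomic status acts through place of residence, adjusting for access removes part of its real effect.

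*Nothing is excluded.* The confounder list is open, and zip code is a listed socioeconomic measure that may already enter the joint model of section 5. A reader might infer that the plan leaves out geography and race; the text supports only that it does not commit to them.

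*Measures may all be single scores.* The Aim 3 text speaks of total and domain scores and uses Spearman correlation, which suggests one df each. On that reading the ranking problem disappears. Unordered occupation is the plausible exception, and the coding is not stated.

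A reader might also infer very high false-positive rates. Rates up to 89% can be produced by assuming a measure–access correlation of 0.7 and an access–outcome correlation of 0.4. The preliminary correlations are called strong, but no coefficient is given, and recruiting mainly from two clinics may narrow the range of access and so favour the lower figures.

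**Conclusion.** The concern holds as a minor one. The Aim 3 text states a raw r² comparison over models whose named covariates leave out the two explanations that the plan itself raises, and a better-defined analysis is available from variables already in the plan. The whole-model r² point holds under any coding if that is the r² reported. The ranking point (about 40% against 16%) applies only where measures differ in df. The confounding point (about 8–20% against 5%) requires geography to be a confounder and uses assumed correlations.

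The documents do not support the stronger conclusions that Aim 3 is defined as an effect beyond geography and race, or that its ranking will be wrong. The primary outcome, change in treatment satisfaction, is untouched. Two limits remain whatever model is used. Inclusion criterion 4 admits only black or Latino patients, so the black versus non-black contrast in section 4 cannot be re-examined. Recruitment mainly from two clinics may leave little variation in access.

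**What to change.** In section 6, Analysis plan, Aim 3:

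- State the coding and df of each socioeconomic measure.
- Fit one base model in the same patients for every measure: age, Charlson index, black/Latino group and the zip code-derived access score.
- Add each measure in turn. Report its coefficient(s) with 95% confidence intervals and the increment in adjusted r² over the base, shown even when negative.
- Report the same results without the access score alongside, since socioeconomic status may act partly through residence.
- State whether zip code is the geographic adjuster or a candidate measure in this analysis.
- Reconcile the one joint model of section 5 with the several models of section 6, for example by also reporting the joint model.
- State the two limits given in the verdict.

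**Cost.** No new data are needed, since zip code and black/Latino self-identification are already in the plan. Deciding the role of zip code may change the list of candidate measures. Precision falls somewhat: at a measure–access correlation of 0.5, access alone widens the interval by 1/√(1 − 0.25) = 1.15, and about 1.17 in simulation with black/Latino group also added (1.06–1.41 for correlations of 0.3–0.7). Power for a true standardised effect of 0.3 falls from about 93% to 83% if access has no effect of its own. Reporting both versions makes this visible. Adjusted r² reduces chance misranking at n = 100 but does not remove it.

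### Aim 3 compares socioeconomic measures on r² point estimates with no interval or test for the differences, so with 100 patients close competitors are not reliably separated and the output would not show it

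*Combined protocol and SAP*

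**What the plan says.** Section 5 states Aim 3 as a comparison between measures: "Identify specific socioeconomic characteristics most strongly associated with PGx drug prescription rates". It sets the sample by saying the model is to "determine which social determinants most associate with PGx drug prescription rate within the 100 patients from Aim 1". Table 1 lists five socioeconomic measures: SEI, occupation, education level, household income and household zip code.

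The Aim 3 paragraph of the Analysis plan (section 6) has three steps:

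- Univariate: "Comparisons will be completed in univariate analyses via Spearman's correlation test".
- Multiple regression adjusted for confounders, with age and the Charlson index as examples.
- Variation explained: "we will estimate the proportion of variation in PGx prescription rate that can be explained by each socioeconomic measure by comparing coefficients of determination".

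The Aim 1 paragraph of the same section sets two-sided P≤0.05 for all analyses. No interval for r², test of a difference in r², resampling, multiplicity adjustment or Aim 3 sample-size calculation is given. Section 5 also speaks of "individual measures of socioeconomic status in a single predictive model", whereas the Analysis plan works "by comparing coefficients of determination (r^2) in each model".

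**The concern.** To say that one measure is more strongly associated than another is a statement about a difference. The only tool the plan offers for that difference is to set sample r² values side by side. The significance tests answer another question, namely whether each measure is associated at all. Two measures can both be clearly non-zero and still be in the wrong order.

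The study is meant to supply preliminary data for larger studies and funding applications. A determinant put first by sampling error could steer that work, and a reader shown only r² values could not tell this from a well-supported ordering.

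**Working it through.** **Inputs from the documents.** N = 100 (section 5, Aim 3); five measures (Table 1); two-sided 0.05 with no stated adjustment (Analysis plan). There is no Aim 3 power or precision figure to reproduce.

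**Assumptions not in the documents.** Each measure enters as one continuous term; normal data; equal pairwise correlation ρ among measures (0 to 0.7); Pearson r² without covariates; true r² values as listed. Repeated simulation runs agree to within about 2 percentage points.

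**1. Significance threshold at N = 100.** Critical r = t/√(98 + t²) with t = 1.984. This is 1.984/√101.94 = 0.197, so r² must reach about 0.039.

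**2. No true association.** For k independent measures, the chance that at least one is significant is 1 − 0.95^k: 14.3% for k = 3, 18.5% for k = 4 and 22.6% for k = 5. For k = 5, simulation gives about 21% at ρ = 0.3, 18.5% at ρ = 0.5 and 15% at ρ = 0.7. Across runs and values of ρ the range is about 15% to 24%. The largest r² has a median near 0.02 and a 95th percentile near 0.06.

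**3. One measure truly best, the other four equal.** Share of trials in which the best measure has the largest sample r² (ρ = 0.3 to 0.5; guessing would give 1/5 = 20%):

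| True r², best v others | Best ranks first |
|---|---|
| 0.05 v 0.02 | about 50–55% |
| 0.09 v 0.04 | about 57–65% |
| 0.10 v 0.05 | about 55–60% |
| 0.15 v 0.05 | about 82–88% |
| 0.20 v 0.05 | about 93–97% |

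In the 0.09 v 0.04 row some measure is significant in about 93% to 96% of trials, so requiring significance does little to protect the ordering. At ρ = 0.3, the correct share in that row rises from 57% at N = 100 to 72% at N = 200 and 89% at N = 400.

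**4. Precision of one r².** For an observed r = 0.3 (r² = 0.09), Fisher's z = 0.3095 with half-width 1.96/√97 = 0.199. Back-transformed, r runs from 0.110 to 0.469, so r² runs from 0.012 to 0.220. An interval that wide holds both 0.04 and 0.20.

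**5. Effect of the single-term assumption.** Unadjusted r² for an unrelated measure with d terms averages d/99: 0.010 for one term and 0.040 for four. If one of the five measures took four terms, it would have the largest r² in about 69% of trials with no true association, instead of 20%. Occupation and zip code could be coded that way, so single terms are the kinder assumption.

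**The case against.** **The plan does test associations.** A reader might infer that Aim 3 makes no allowance for sampling error and names a leader every time, even when nothing is related. The documents do not support that. Spearman tests are specified and P≤0.05 applies to all analyses. If significance is required before a measure is ranked, most trials with no true association yield no candidate. What stands is that the plan does not state this link, and that the tests compare each measure with zero only.

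**No winner rule is written.** The text estimates variation explained, and the aim speaks of characteristics and determinants in the plural. A rule that the largest r² wins is an inference from reading the aim with the analysis sentence. Even so, the aim asks which measures associate most, and the r² comparison is the only between-measure method offered.

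**The ranking is informative.** A reader might infer that it carries almost no information at this sample size. That fails for wide gaps (82% or more correct from 0.15 v 0.05 upward), and even 57% is nearly three times chance. The weakness is confined to close competitors.

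**This is a pilot.** Aim 3 is not the primary outcome, which is change in treatment satisfaction, and no treatment decision rests on it. This stands and limits the severity.

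**Conclusion.** The concern holds in a limited form. Aim 3 poses a between-measure question and answers it with r² point estimates that carry no stated uncertainty for their differences. The significance tests do not fill the gap: they are against zero, unadjusted for the several measures, and not tied to the ordering.

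The size depends on the unknown true gap. The best measure ranks first in roughly half to two-thirds of trials when competitors are close and in more than nine-tenths when it is far ahead. The documents give no basis for expecting either case. All simulated figures rest on the assumptions listed, chiefly five single-term measures with equal correlation. Severity is minor: this is a cheap improvement to an exploratory aim.

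**What to change.** In the Aim 3 paragraph of the Analysis plan, add a paired bootstrap over patients that refits every model in each resample. Report:

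- each measure's r² with a 95% interval;
- the interval for the r² difference between the top measure and the runner-up, with both fixed from the original sample;
- the share of resamples in which each measure ranks first.

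Describe any ranking as exploratory, and state that the measures are not separated when the difference interval includes zero. The same edit should say which models' r² is meant, since section 5 describes one model and the Analysis plan several.

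The interval should not be a hard rule on whether a leading measure may be mentioned. In simulation, a difference interval lying above zero occurs in only about 2% to 4% of trials at 0.09 v 0.04. It occurs in about 10% to 18% at 0.15 v 0.05, where the plain ordering is right in 82% to 88%. A strict rule would suppress many correct leads.

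The cost is a few lines of R on data already collected and a sentence or two in the plan. The downside is that with 100 patients the intervals will usually show that the measures cannot be separated.
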